12.3 Statistical Methods

We will compare baseline and follow-up results for each treatment group using analysis of repeated measures with Proc Mixed in SAS. The measures of endothelial phenotype (EC insulin-signaling) and vascular function (flow-mediated dilation) will be our dependent variables and treatment, period, and sequence will be the main independent measures. That is the variables are denoted as y_{ijk} is the observation for the i^{th} sequence ($i=1,2$) j^{th} subject ($j=1,2,\dots,n$) k^{th} period ($k=1,2$).

The model can be described by:

$$y_{ijkl} = \beta_0 + \beta_1 X_{treat} + \beta_2 X_{period} + \beta_{12} X_{treat} X_{period} + s_{ij} + \varepsilon_{ijk}$$

s_{ij} is a random subject effect term and is assumed to be independently and identically distributed with $N(0, \sigma_s^2)$

ε_{ijk} is an error term and is assumed to be independently and identically distributed with $N(0, \sigma^2)$

Two dummy variables are introduced as:

$X_{treat} = 1$ if the subject is in treatment B, and $X_{treat} = 0$ otherwise;

$X_{period} = 1$ if the subject is in period 2, and $X_{period} = 0$ otherwise;

Model fitting and inference will follow conventional REML analysis in the Proc Mixed procedure in SAS. The between-subject variation includes a carry-over treatment effect and between-subject residuals. The within-subject variation includes direct treatment effect, period effect, and within-subject residuals. A significant period effect reflects evidence of carry-over effect. A significant within-subject treatment effect is consistent with differences between the two treatments adjusting for carry-over and period effect. In exploratory analyses, we will evaluate for effect modification by sex and race. We will evaluate additional exploratory outcomes in a similar fashion.

Analysis Datasets: The intention-to-treat (ITT) analysis dataset will be the source of data for primary analyses. This will include all randomized participants regardless of actual receipt or compliance with therapy. The per protocol analysis will be conducted based on adherence to assigned treatment (defined as more than 80% based on pill returns). Use of Proc Mixed analyses allows all participants to be included if they contribute any data to the analysis dataset.

Baseline Descriptive Statistics: All variables will be summarized using mean, median, standard deviation, and range (for continuous variables) and frequency (for categorical variables). Treatment order groups will be compared with respect to baseline characteristics to verify randomization balance.

13 Ethics/Protection of Human Subjects

This study is to be conducted according to applicable US federal regulations and institutional policies (which are based in federal regulations, guidance, and ICH Good Clinical Practice guidelines).

This protocol and any amendments will be submitted to the Boston Medical Center and Boston University Medical Campus IRB, for formal approval of the study conduct. The decision of the IRB concerning the conduct of the study will be made in writing to the investigator. A copy of the initial IRB approval letter will be provided to the sponsor before commencement of this study.

All subjects for this study will be provided a consent form describing this study and providing sufficient information for subjects to make an informed decision about their participation in this study. The consent form will be submitted with the protocol for review and approval by the IRB. The consent of a subject, using the IRB-approved consent form, must be obtained before that subject is submitted to any study procedure. Consent will be documented as required by the IRB.

14 Literature References

2. Collaboration NCDRF. Worldwide trends in diabetes since 1980: a pooled analysis of 751 population-based studies with 4.4 million participants. *Lancet*. 2016;387:1513-1530.

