4.2.1 Primary Outcome Measures

The primary outcome is insulin-mediated eNOS phosphorylation measured in ECs. The percentage change in the phosphorylation of eNOS is measured using quantitative immunofluorescence microscopy in EC collected before and after each treatment period.

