4.2.2 Secondary Outcome Measures

Key Secondary Outcome: Flow-mediated dilation of the brachial artery measured by ultrasound. We measure the percentage change in the diameter of the brachial artery before and after a 5 minute cuff occlusion on the arm as a measure of endothelial function. We will measure before and after each treatment period.

Other secondary Endpoints:

- Arterial stiffness measured by tonometry
- Microvascular dilator function by EndoPAT
- Plasma measures of noncoding RNA
- EC measures of noncoding RNA
- EC measures of coding RNA
- Circulating biomarkers of vascular health including BNP and CRP
- Fasting glucose, insulin, and lipid profile
- Body weight and waist circumference

5 Study Design

5.1 Overall design:

The overall design is a single center randomized, double-blind, cross-over, placebo-controlled study of dapagliflozin (an SGLT2 inhibitor) compared to placebo in patients with T2DM. Each treatment period lasts 6 weeks with a 2 week washout period between study treatments. The study intervention is 10mg per day of dapagliflozin compared to placebo. Vascular health measures including EC, vasodilator function, and circulating biomarkers will be measured before and after each treatment period. An outline of the study visits and procedures is in the appendix. A cross-over design is being used in order to be able to be able to minimize variability by comparing within individual effects. Prior studies from our group and others have not shown carry-over effects with regards to the primary outcome measures.

Subjects will be randomized 1:1 ratio to receive SGLT2 inhibitor (dapagliflozin 10mg/day) and then placebo or vice versa. Treatment order will be block randomized in block sizes of 2 or 4. 50 subjects will be consented with the goal of randomizing 42 and having 35 study completers.

Participants will be adult men and women who are outpatients with established T2DM. All participants will receive both study interventions.

The study intervention is an FDA-approved medication used in the FDA-approved study population with the objective of identifying mechanisms of cardiovascular health effects thus the study does not fit into an FDA defined trial Phase.

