12.2 Sample Size Determination

The primary analysis for this randomized cross-over study will be comparison of the primary endpoint, EC insulin-signaling, and the secondary outcome, flow-mediated dilation, during the dapagliflozin treatment period compared to the placebo treatment period. These continuous outcomes were used to power the study.

In our prior work, we have reported that patients with T2DM have an EC insulin response of $-10 \pm 9\%$ and a flow-mediated dilation response of $6.5 \pm 4.3\%$. These measures are expected to be similar in patients enrolled in the present study. An effect size of (how much) was used to calculate the expected sample size for the study.

The analysis will use a an analysis of repeated measures using Proc Mixed in SAS with conventional REML analysis to compare baseline and follow-up results for each treatment group with an overall significance level two-sided alpha=0.025 given the planned primary and secondary endpoints. In order to ensure 90% power to detect an effect size of 0.25 for each outcome, the study needs to

have at least 35 participants who complete the study (SD of differences, $\sigma=5.8\%$ for EC insulin-signaling and 3.5% for flow-mediated dilation). We estimate that 85% of consented participants (50) will be randomized (42). We estimate that 7% of participants will not complete and 83% will complete (35). The sample size has been calculated using NQuery Advisor [version 8.7.2.0, Statistical Solutions, San Diego, CA].

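### Sections 12.2 and 12.3 do not fix what y is or which difference the SDs describe, and β1 of the printed model is not the within-subject treatment effect

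*Combined protocol and SAP*

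**What the plan says.** - **Measurements.** Section 5.1, Section 9 and the Schedule of Events put the EC and vascular measures at Visits 1 to 4 (weeks 0, 6, 8 and 14). That is a before and an after value in each period, so four values per subject.
- **Comparison.** Section 12.3 opens with "We will compare baseline and follow-up results for each treatment group using analysis of repeated measures with Proc Mixed in SAS", and Section 12.2 has the same idea: "conventional REML analysis to compare baseline and follow-up results for each treatment group". Section 12.2 also describes the primary analysis as the outcome "during the dapagliflozin treatment period compared to the placebo treatment period".
- **Model.** Section 12.3 states that "y_{ijk} is the observation for the i^{th} sequence", together with subject and period (k = 1, 2). The equation has treatment and period as 0/1 dummies, their product, a random subject effect and an error. Its response carries a fourth subscript, l, that is never defined. It has no baseline covariate and no before/after term. The text then says that a within-subject treatment effect will be interpreted.
- **Outcome definitions.** Section 4.2.1: "The percentage change in the phosphorylation of eNOS is measured using quantitative immunofluorescence microscopy in EC collected before and after each treatment period". Section 4.2.2, for FMD: "We measure the percentage change in the diameter of the brachial artery before and after a 5 minute cuff occlusion".
- **Variability.** Section 12.2 gives 5.8% and 3.5% as SDs of differences without naming the difference. It also reports from prior work that "patients with T2DM have an EC insulin response of" −10 ± 9%, and an FMD of 6.5 ± 4.3%.

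**The concern.** The wording and the equation describe different analyses. Comparing baseline with follow-up in each treatment group is a before/after comparison within treatment. The randomised question is dapagliflozin against placebo within subject. The equation has room for only one number per period, so four values must become two by a rule that is not given.

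Section 4.2.1 does not supply the rule. Its percentage change can be the response to insulin at one visit, which fits the synopsis, the prior-work figure in Section 12.2 and the parallel FMD definition. It can equally be the change over a treatment period.

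Two analysts could therefore follow Section 12.3 faithfully, fit different primary analyses and report different estimates, and the plan could not say which was intended. The sample size also rests on SDs that may belong to a different quantity from the one analysed. And an analyst who tests the treatment coefficient exactly as printed would lose the within-subject precision for which Section 5.1 chose the cross-over design.

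**Working it through.** **1. The plan's own figure.** Inputs from Section 12.2: two-sided alpha 0.025, power 90%, effect size 0.25, 35 completers. Reading 0.25 as effect divided by SD of differences, the noncentral t gives 202 completers, and power of about 0.21 at 35. The 35 is not reproduced on that reading. Reading 0.25 as Cohen's f (an effect of half the cross-sectional SD: 0.5 × 4.3 = 2.15 points), with 3.5% as the SD of a single difference, gives 36 for FMD but 24 for EC. So the effect size is under-defined; 35 is not shown to be wrong.

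**2. A common yardstick.** Assume 18 and 17 completers per sequence.
- SE of the within-subject contrast = (SD/2) × √(1/18 + 1/17) = (SD/2) × 0.338, with 33 df.
- For EC: 2.9 × 0.338 = 0.98. For FMD: 1.75 × 0.338 = 0.59.
- The effect giving 90% power is 0.62 SD (0.6197 unrounded): 3.59 points for EC and 2.17 for FMD.

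This effect is back-solved, not stated in the plan.

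**3. If y and the SDs do not match.** Let r be the correlation between the baseline difference (Visit 1 against Visit 3) and the end-of-period difference (Visit 2 against Visit 4), with equal variances. The documents do not give r. The variance of the change-score difference relative to the end-value difference is 2(1 − r).

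| r | 0 | 0.3 | 0.5 | 0.6 | 0.7 |
|---|---|---|---|---|---|
| **SDs are of end values** | | | | | |
| Change scores, variance ratio | 2.0 | 1.4 | 1.0 | 0.8 | 0.6 |
| Change scores, power at 35 | 0.60 | 0.77 | 0.90 | 0.96 | 0.99 |
| Completers for 90% | 68 | 48 | 35 | 29 | 23 |
| Baseline-adjusted, power | 0.89 | 0.92 | 0.96 | 0.98 | 0.996 |
| **SDs are of change scores** | | | | | |
| Unadjusted end values, power at 35 | 0.997 | 0.97 | 0.90 | 0.82 | 0.69 |
| Completers for 90% | 19 | 26 | 35 | 44 | 57 |
| Baseline-adjusted, power | 0.996 | 0.98 | 0.96 | 0.95 | 0.93 |

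Where y and the SDs match, power is 0.90 throughout. The baseline-adjusted rows come from 20,000 simulated trials per r. Their variance relative to unadjusted end values agrees with (1 − r²) × 32/31, which is 1.03 at r = 0.

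**4. What β1 estimates.** The expected cell values in the printed model are:
- period 1, treatment A: β0
- period 1, treatment B: β0 + β1
- period 2, treatment A: β0 + β2
- period 2, treatment B: β0 + β1 + β2 + β12

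So β1 is B minus A in period 1, and those two cells hold different subjects. The within-subject effect averages the two periods: ½[β1 + (β1 + β12)] = β1 + β12/2.

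SE and power of β1 with the effects from step 2:
- y a single-visit value, EC: 9 × 0.338 = 3.04, against 0.98 for the within-subject contrast; power 0.13.
- y a single-visit value, FMD: 4.3 × 0.338 = 1.45, against 0.59; power 0.21.
- y a change score with the stated SDs, changes uncorrelated between periods, EC: per-period SD 5.8/√2 = 4.10; SE 4.10 × 0.338 = 1.39; power about 0.60. FMD gives the same power. For correlations between changes of −0.3 to 0.3 the power is 0.73 to 0.44.

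**5. Baseline adjustment if a drug effect persists at Visit 3.** Assume a residual of half the effect (1.8 EC points). The adjusted estimate averages 3.59, 3.87, 4.03 and 4.22 at r = 0, 0.3, 0.5 and 0.7, against a true 3.59. The unadjusted estimate stays at 3.59 and change scores give about 4.5. In simulation, for r = 0.3 to 0.7, the gap between adjusted and unadjusted estimates averages 0.27 to 0.65 with an SD of 0.37 to 0.71, and has the wrong sign in 17 to 21% of trials.

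**The case against.** The best defence is that the baselines do have a role. Both sections say they are compared with follow-up, and the stray l may have been meant to index the visit within period, with both visits as outcomes. A reader might infer that the plan ignores its baselines; the text does not support that. What remains is that no visit term appears, the error term has only three subscripts and l is undefined, so this third reading cannot be fitted from the equation either. It is not quantified above.

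Second, Section 12.3 says it will interpret a within-subject treatment effect, so the team may never intend to test β1. That is fair, and it means 0.13 and 0.21 should not be read as the trial's power. They also hold only for single-visit values. But the printed equation and the stated inference still disagree.

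Third, the power table rests on a back-solved effect and an unknown r. Under the plan's own error structure (random subject plus independent errors) r is 0, and baseline adjustment then gains nothing over unadjusted end values. This stands: the table shows what the ambiguity can do, not what it does.

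Fourth, unadjusted end values, a prespecified change score and a joint model of all four visits are each defensible. That also stands, so baseline adjustment is offered below as an option only.

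**Conclusion.** The concern holds as an undefined primary variable and a mismatch between the equation and the stated inference. The definition of y, the place of the Visit 1 and Visit 3 values, the index l and the meaning of the two SDs all need to be stated. If y and the SDs refer to different quantities, power at 35 completers lies between 0.60 and 0.997 over r = 0 to 0.7, given 18/17 completers, equal variances and an effect of 0.62 SD. The direction is not fixed by the documents.

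A reader might infer that the trial is underpowered or that 35 is wrong. The documents do not support this: if y and the SDs match and the within-subject contrast is tested, power on this yardstick is 0.90, and some mismatches raise it. The β1 problem follows from the printed coding and needs no assumption about r; only its power figures depend on what y is. This should be settled before unblinding.

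**What to change.** In Sections 12.2 and 12.3:

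- Replace the per-group baseline/follow-up comparison with the within-subject dapagliflozin-versus-placebo contrast.
- Fit treatment, period and sequence without the treatment-by-period product, or keep the product and test β1 + β12/2 explicitly. Do not test β1 of the printed model.
- Define y_ijk, for example as the end-of-period value (Visit 2 for k = 1, Visit 4 for k = 2). Define or remove l.
- State which difference 5.8% and 3.5% describe, so that the model and the sample size use the same quantity.

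These are wording changes and need no new data.

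Optionally, adjust for the period baselines already collected at Visits 1 and 3, entered as subject mean and deviation from it. For a subject with one baseline, use it as the mean and set the deviation to 0. This keeps the promise in Section 12.3 that "Use of Proc Mixed analyses allows all participants to be included if they contribute any data to the analysis dataset". On the yardstick above, adjustment holds power at or above about 0.89 under both SD readings for r = 0 to 0.7. It costs one or two degrees of freedom and about 3% in variance at r = 0, brings no gain over unadjusted end values below about r = 0.2, and biases the estimate upward if a drug effect persists at Visit 3 and r is above 0. Section 5.1 reports no carry-over in prior studies. Report the unadjusted end-of-period contrast alongside it, without claiming that the comparison would reliably detect such bias.

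### The model equation in section 12.3 omits the sequence term its text names and fixes no test; its printed treatment coefficient is not the within-subject effect the plan targets

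*Combined protocol and SAP*

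**What the plan says.** - Section 12.3 states that "treatment, period, and sequence will be the main independent measures".
- The equation in the same section has an intercept, treatment, period and their product ("X_{treat} X_{period} + s_{ij"), a random subject term and an error. Sequence appears only as the index i.
- Both dummies are 0/1. Treatment is coded 1 "if the subject is in treatment B, and" 0 otherwise, and period is coded 1 for period 2. The section does not say which treatment is B.
- No coefficient, contrast, least-squares mean or Type 3 test is named as the primary or key secondary test.
- The target is described in words: "The within-subject variation includes direct treatment effect, period effect, and within-subject residuals", and "A significant within-subject treatment effect is consistent with differences between the two treatments adjusting for carry-over and period effect".
- Section 12.2 sizes the trial on an SD of differences and compares outcomes "during the dapagliflozin treatment period compared to the placebo treatment period". Section 5.1 justifies the cross-over by within-person comparison and says that earlier studies showed no carry-over on the primary outcome measures.
- On the response variable, the text of section 12.3 indexes y by sequence, subject and period, while the equation prints a fourth index l that is not defined. The section opens with "We will compare baseline and follow-up results for each treatment group", and section 4.2.1 measures "EC collected before and after each treatment period". How the period baselines enter the model is not stated.

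**The concern.** Section 12.3 is the only model specification, and it covers both the primary and the key secondary outcome. Its words and its equation name different covariates. With 0/1 coding and a product term, the coefficient on treatment is the treatment difference when period equals 0, that is, in period 1 only. In an AB/BA design the two treatments are taken by different people in period 1, so this coefficient gives up the pairing for which the cross-over was chosen. Two analysts could each follow section 12.3 in good faith and report different p-values for the primary endpoint.

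The carry-over sentence adds a second difficulty. It asks for one effect that is both within-subject and adjusted for carry-over. A reader would take the within-subject result to be protected against carry-over when it is not.

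**Working it through.** **Algebra, one value per subject and period.** Write the four cell means as AB1, AB2, BA1, BA2, with the treatment dummy 1 for B and the period dummy 1 for period 2.

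- Printed model: beta_1 = BA1 − AB1, a comparison between subjects. beta_12 = AB1 + AB2 − BA1 − BA2.
- Hence beta_1 + beta_12/2 = ½[(AB2 − AB1) + (BA1 − BA2)], which is the within-subject effect.
- With a sequence dummy equal to 1 for BA, sequence = treatment + period − 2 × (treatment × period). The product model, the sequence model and the two combined all have rank 4, so the fitted means are identical. Replacing the product by sequence makes the treatment coefficient exactly ½[(AB2 − AB1) + (BA1 − BA2)]. Only the meaning of the treatment coefficient changes.

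**Inputs.** From section 12.2: 35 completers, two-sided alpha 0.025, SD of differences 5.8% (EC) and 3.5% (FMD), response SDs 9% and 4.3%. Assumptions: completers split 18/17 by sequence, and 9% and 4.3% are total SDs of one end-of-period value.

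**Standard errors.** Let k = 1/18 + 1/17 = 0.1144.

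- SE(beta_1) = SD × √k
- SE(beta_1 + beta_12/2) = ½ × SD of differences × √k
- Ratio = 2 × SD / SD of differences

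| | SE(beta_1) | SE(within-subject) | Ratio |
|---|---|---|---|
| EC | 9 × 0.338 = 3.04 | ½ × 5.8 × 0.338 = 0.98 | 18/5.8 = 3.1 |
| FMD | 4.3 × 0.338 = 1.45 | ½ × 3.5 × 0.338 = 0.59 | 8.6/3.5 = 2.5 |

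In 150 simulated trials with the EC variances, fitted by REML, the mean SEs were 3.04 and 0.98. The contrast beta_1 + beta_12/2 agreed with the sequence-model coefficient to rounding error.

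**Dependence on y.** In general the variance ratio is 2/(1 − rho), where rho is the correlation of y between periods. The assumed SDs imply rho = 1 − 5.8²/(2 × 9²) = 0.79 for EC and 1 − 3.5²/(2 × 4.3²) = 0.67 for FMD. If y is a within-period change, rho is not given. Over an assumed range of 0.5, 0, −0.5 the variance ratio is 4.00, 2.00, 1.33, so the SE ratio is 2.0, 1.4, 1.2.

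**Power, for illustration only.** The plan's own figure of 35 completers cannot serve as the anchor. Reading its effect size of 0.25 as a difference over the SD of differences gives 202 completers for 90% power, and the scale of 0.25 is not defined; that is a separate matter. I therefore back-calculated the difference at which 35 completers give the within-subject test 90% power: 0.62 SD of differences, or 0.62 × 5.8 = 3.6 points (EC) and 0.62 × 3.5 = 2.2 points (FMD). At that difference a test of beta_1 has these powers:

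- End-of-period values: about 13% (EC) and 21% (FMD).
- Change scores, rho 0.5, 0.25, 0, −0.25, −0.5: 32%, 47%, 60%, 71%, 79%.

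**Carry-over.** Let the treatment effect be T. Let carry-over in the dapagliflozin-first group add c_b to the period-2 baseline and c_f to the period-2 follow-up.

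- End-of-period values: the within-subject contrast estimates T − c_f/2. With c_f = 0.2T this is 0.90T, and power falls from 90% to about 82%. beta_1 uses only period 1 and is unaffected.
- Change scores: it estimates T − (c_f − c_b)/2. With carry-over of 0.2T at follow-up only, at baseline only, or equally at both, the result is 0.90T, 1.10T or 1.00T.

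**Stacked rows.** If baseline and follow-up rows were stacked with treatment coded 0 at baseline, the product and sequence models would no longer be equivalent (ranks 4 and 4, combined 5). With no baseline/follow-up term, a change common to both periods of 0.2T would move beta_1, beta_1 + beta_12/2 and the sequence-model coefficient to about 1.13T. Adding that term restores 1.00T.

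**The case against.** The strongest reply is that nothing in the plan says beta_1 will be tested. Section 12.3 rests its conclusion on a within-subject treatment effect, section 12.2 sizes on differences, and section 5.1 gives the within-person rationale. An analyst who declares treatment and period as CLASS variables in Proc Mixed and takes period-averaged least-squares means gets beta_1 + beta_12/2 without further instruction. This stands. A reader might infer that the plan commits the trial to the wrong test; the documents show only that the test is left open.

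A reader might also infer that the product makes this a different or invalid model. With one value per subject and period it does not, because the fitted means are the same. What has substance is the unnamed contrast and the conflict between words and equation.

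It can be said in favor of beta_1 that it is free of carry-over, so it meets half of what the prose asks. That is true, but it then fails the other half. The two requested properties are incompatible here, which is a reason to choose one in advance.

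Finally, y is not wholly undefined. The text and the error term are indexed by sequence, subject and period, which implies one value per subject and period and sits badly with stacked rows. The extra l may be a typing or text-extraction slip. What remains open is mainly end-of-period value against within-period change.

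**Conclusion.** The point holds as a specification gap that should be fixed. The mismatch between the listed covariates and the equation, and the absence of a named test, are plain on the page and need no assumption. That beta_1 is a between-subject comparison follows from the coding, given one value per subject and period.

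The loss of precision arises only if numeric dummies are used and beta_1 is read as the test. Its size rests on assumptions about y, its SD and rho: a standard error 3.1 and 2.5 times larger under the end-of-period reading, and 1.2 to 2.0 times larger over the assumed range for change scores. It would be tempting to headline a fall from 90% to about 13% power. The documents do not support any single figure, because they do not settle y and the comparison difference is back-calculated.

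The claim of adjustment for carry-over is wrong for the within-subject contrast with one value per subject and period. It would also go too far to say that this contrast always keeps half of any differential carry-over. That is true for end-of-period values, or if carry-over is defined on y itself. For change scores the size and direction depend on where the carry-over acts.

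**What to change.** 1. Make the equation match the text: fixed treatment, period and sequence, random subject within sequence, and treatment coded 1 for dapagliflozin. Name that treatment coefficient as the primary and key secondary test. Alternatively, with one value per subject and period, keep the product and prespecify beta_1 + beta_12/2.
2. State whether y is the end-of-period value or the within-period change, say how the period baselines enter, and correct the fourth index on y. If rows are to be stacked instead, use the sequence model and add a baseline/follow-up term.
3. Replace the carry-over wording. Say that the within-subject contrast adjusts for period and assumes negligible differential carry-over, as section 5.1 argues. State that it keeps half of any such carry-over only if y is the end-of-period value or carry-over is defined on y itself.

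This costs one equation and a few sentences in section 12.3, before unblinding, with no added data. The downside is that the chosen contrast relies on the no-carry-over position that section 5.1 already takes.

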11.4 Study Records Retention

Study records will be retained for at least seven years after completion of the study. Documentation of informed consent of subjects will be retained for at least seven years after the study is closed. Such records will be preserved in hardcopy, electronic or other media form and will be accessible for inspection and copying by authorized individuals.

12 Statistical Plan

The overall study design is an AB/BA two-treatment, two-period cross-over trial.

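### Section 12.3 reads a significant period effect as carry-over and calls the treatment effect carry-over-adjusted; an AB/BA design supports neither statement

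*Combined protocol and SAP*

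**What the plan says.** Section 12 states the design: "The overall study design is an AB/BA two-treatment, two-period cross-over trial". Section 12.3 says that "treatment, period, and sequence will be the main independent measures". The printed equation, however, has 0/1 indicators for treatment and period, their product (coefficient β12) and a random subject effect, with no separate sequence term.

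Four sentences of interpretation follow. The first two divide the variation: carry-over is assigned to the part between subjects, while treatment and period are assigned to the part within subjects. The third gives the rule at issue: "A significant period effect reflects evidence of carry-over effect". The fourth turns to the treatment contrast and claims an adjustment for more than period: "A significant within-subject treatment effect is consistent with differences between the two treatments adjusting for carry-over and period effect".

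Section 12.3 does not say that β12, or sequence, is the term that carries information on carry-over. It attaches no action to a significant period effect. Section 5.1 justifies the cross-over by its within-individual comparison, specifies a 2-week washout, and says that earlier studies saw no carry-over.

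**The concern.** The third sentence conflicts with the two before it. Those place carry-over between subjects and period within subjects; the third then uses the within-subject term to diagnose the between-subject one. A common drift between periods (season, familiarity with the procedures, assay drift) moves the period effect with no carry-over at all. Conversely, carry-over can be present while the period effect is near zero.

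The fourth sentence credits the within-subject treatment effect with an adjustment it does not make.

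At stake is the report's statement about carry-over, which can be wrong in either direction: a harmless trend reported as carry-over, or a non-significant period effect taken as reassurance. Section 5.1 rests the design on absent carry-over, so readers will look here for confirmation. There is also a practical risk. An analyst who reads the treatment coefficient straight from the printed model gets a between-subject comparison and not the within-subject effect the sentence names.

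**Working it through.** The plan gives no figure for trend or carry-over, so there is none to reproduce. The check is algebra on the cell means, followed by rejection rates on the plan's own variances.

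**Cell means.** Let μ be the mean, π the period effect (2 minus 1), τ the treatment effect (B minus A), and λA, λB the carry-over of A and B into period 2.

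| Sequence | Period 1 | Period 2 |
|---|---|---|
| AB | μ | μ + π + τ + λA |
| BA | μ + τ | μ + π + λB |

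Four cell means cannot identify five parameters (rank 4). The within-subject differences, period 2 minus period 1, are τ + π + λA for AB and −τ + π + λB for BA. Hence:

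- averaged period contrast (half-sum) = π + (λA + λB)/2
- within-subject treatment contrast (half-difference) = τ + (λA − λB)/2
- difference between sequence totals = λA − λB, aliased with any sequence difference

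**The printed model.** Solving the 0/1-coded equation gives β1 = τ, β2 = π + λB and β12 = λA − λB. So β2 also mixes trend with carry-over. The documents do not say which treatment is A; if it is dapagliflozin, β2 contains none of its carry-over. β1 is free of carry-over only because it is the period-1 comparison between subjects. The within-subject contrast is β1 + β12/2.

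A REML fit of the printed model to one simulated data set of 35 completers bears this out. β1 + β12/2, the treatment coefficient without β12, the treatment coefficient with a sequence indicator, and the hand-computed half-difference all equal 3.586. β1 alone equals the period-1 between-subject difference, −3.911.

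**Inputs from Section 12.2.** 35 completers, taken as 18/17; SD of differences 5.8 (EC insulin-signaling) and 3.5 (FMD), taken as the SD of the within-subject between-period difference; single-measure SD 9 and 4.3. The plan sets no level for the period test, so I use the level stated for the endpoints: "overall significance level two-sided alpha=0.025 given the planned primary and secondary endpoints".

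**Standard errors.** √(1/18 + 1/17) = 0.3382.

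- Averaged period or within-subject treatment contrast: 0.5 × 5.8 × 0.3382 = 0.98 (EC); 0.5 × 3.5 × 0.3382 = 0.59 (FMD).
- Literal β1 or β2, end-of-period values: 9 × 0.3382 = 3.04 (EC); 4.3 × 0.3382 = 1.45 (FMD). These are 3.1 and 2.5 times larger.
- β12: √(4 × 9² − 5.8²) × 0.3382 = 5.76 (EC); √(4 × 4.3² − 3.5²) × 0.3382 = 2.66 (FMD).

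**Harmless trend labelled carry-over** (noncentral t, 33 df; sizes assumed, in units of the SD of differences):

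| Trend | Averaged test | Literal β2, EC | Literal β2, FMD |
|---|---|---|---|
| 0.1 SD | 5% | 3% | 3% |
| 0.2 SD | 14% | 4% | 4% |
| 0.3 SD | 30% | 5% | 6% |
| 0.5 SD | 73% | 9% | 14% |

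**Cases the averaged period test cannot tell apart.**

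- Trend 0.25 SD, no carry-over: contrast 0.25 SD, flagged in 21%, no bias.
- Dapagliflozin-only carry-over 0.5 SD, no trend: contrast 0.5/2 = 0.25 SD, flagged in 21%. The treatment estimate shifts by 0.25 SD, which is 1.45 EC points (0.25 × 5.8) or 0.88 FMD points (0.25 × 3.5).
- The same carry-over with an opposing trend of 0.25 SD: contrast 0, flagged in 2.5%, same shift.

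Simulation with 20,000 trials per scenario agrees with the averaged-test rates within 1 point.

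**Direction of the shift.** With end-of-period values, a positive dapagliflozin carry-over λ lowers the dapagliflozin-minus-placebo estimate by λ/2. With change from each period's baseline, a residual at Visit 3 that fades by Visit 4 raises it by half that residual.

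**The case against.** The strongest case against is about weight. Nothing is gated on the period test, and the sentence alters neither the primary estimate nor its p-value. The two preceding sentences give the standard decomposition, which suggests loose wording more than a wrong analysis. This stands, and it is why the point is a correction of text and not a fault in the design.

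The larger percentages belong to the averaged period test; for the literal β2 they are 3–9% (EC) and 3–14% (FMD). This also stands. The documents do not settle which reading applies, so both are shown.

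The carry-over sizes have no support in the documents. By the Schedule of Events, dapagliflozin given first stops at week 6 and Visit 4 is at week 14, so a 0.5 SD residual in an end-of-period value 8 weeks later would be surprising. That is fair: the shifts are illustrations and not predictions, and they would exist whatever the sentence said. If the endpoint is change from each period's baseline, though, the relevant gap is the 2 weeks to Visit 3.

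Finally, β1 in the printed model is indeed free of carry-over, so the fourth sentence could be defended as a description of β1. But β1 is not within-subject, and the sentence says it is. The two descriptions fit no single contrast, so the plan has to name one.

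**Conclusion.** The concern holds. Both sentences are wrong as written, they conflict with the two before them, and no other section corrects them. The algebra depends only on the AB/BA design and the printed coding. The rates depend on assumed trend and carry-over sizes, 18/17 completers, a 0.025 level for the period test, and the plan's SDs read as described. On the averaged reading a harmless trend of 0.1 to 0.5 SD would be called carry-over in 5% to 73% of trials, and a carry-over that shifts the treatment estimate by 0.25 SD can go unflagged beyond the nominal 2.5%. Taking β1 as the treatment effect would cost a factor of 3.1 (EC) or 2.5 (FMD) in standard error. The point should be fixed before unblinding, but it does not threaten the design.

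**What to change.** In Section 12.3, delete the sentence on the period effect and put in its place:

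> Period is a nuisance term and is not interpreted as carry-over. Differential carry-over is aliased with sequence (β12 in the model); freedom from it rests on the washout.

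In the next sentence, remove the reference to carry-over so that the treatment effect is described as adjusted for period only. Add one line stating that the primary treatment effect is the within-subject contrast averaged over periods, which in the printed coding is β1 + β12/2 and not β1. For completers, dropping β12, or replacing it with the sequence indicator the text already names, gives the same estimate.

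Report the sequence contrast descriptively, with no pre-test used to choose the analysis. The difference between sequences in Visit 3 minus Visit 1 could be added; it is not moved by a common trend. Low power should be acknowledged for both. For a dapagliflozin-only residual of 0.3 or 0.5 SD at the 0.025 level, the sequence contrast detects 3% or 4% (EC) and 4% or 6% (FMD). The Visit 3 comparison detects 8% or 21%, if the plan's SD of differences applies to that pair of visits.

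The cost is two edited sentences and one added line. The sequence contrast comes from the same fit and the Visit 3 data are already collected, so no new procedures and no change in sample size are needed.
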